Integrated Alcohol Disorder and PTSD Treatment

NCT01601067

09/03/2011

Primary Outcome Analyses.

6.H.3. Primary Outcome Analyses. The first primary aim is to evaluate if I-PE will demonstrate greater reduction in PTSD symptoms than SS at post treatment. The statistical model will be a random intercept regression model with treatment condition (I-PE, SS) and a linear term for time (0, 2 months). The primary test of the treatment conditions will be treatment x time interaction effect. We will also test the extent to which gender moderates treatment effect. The model can be expanded to determine an adjusted intervention effect by including additional covariates(e.g., age, ethnicity). This model provides maximum likelihood (ML) parameter estimates; allowing modeling of the covariance error structure data across assessment points.⁹¹

The second primary aim is to evaluate if I-PE will result in greater percent days abstinent (PDA) from substance use at 5 and 8-month follow-up. The statistical model will be a random intercept regression model with treatment condition (I-PE, SS) and a linear term for time (0, 2, 5, 8 months). The primary test of the treatment conditions will be the treatment x time interaction effect. A quadratic effect of time will also be tested to model potential decaying treatment effects. We will test the moderating effect of gender on the treatment effect by testing a treatment x time x gender interaction term in the model. Additional covariates can also be added to the model to determine an adjusted intervention effect.

The primary outcomes will be tested using an intent-to-treat framework. If the extent of missing data is small and the data appear to be consistent with a missing-at-random model (MAR), then the maximum-likelihood analysis using all randomized cases and the observed data is an appropriate method for handling the missing data. In the MAR model the missingness can be a function of the observed covariates and observed outcomes. The MAR assumption is plausible in treatment situations, even in studies such as substance abuse in adolescents.⁹² The critical element when conducting MAR-based analyses is to include variables related to the missingness in the statistical model.⁹² Potential variables we will measure that may be related to study drop out are group assignment, social and familial support, employment status, and income. As a check on the sensitivity of our conclusions to the assumption that the missing data are MAR we will conduct pattern-mixture modeling, which is appropriate with data that is likely MAR.⁹³ The distinction between ignorable (MAR) and non-ignorable missingness (missing not at random; MNAR) is generally not empirically testable and we acknowledge the possibility that data may be missing not at random. Therefore, we propose to perform MNAR sensitivity analyses using pattern mixture models. With 3 follow-up assessment points there are 9 potential missing data patterns that can emerge. Some patterns will likely have small numbers of cases precluding parameter estimation for these patterns separately. In this case we will apply the Hedeker and Gibbons (1997) approach that combines missing data patterns to estimates model parameters that are conditional on the missingness using a binary variable in the model to denote missing data at one or more time points.

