Integrated Alcohol Disorder and PTSD Treatment

NCT01601067

04/14/2016

Objectives

The primary aim will be to evaluate the effects on alcohol use and PTSD symptoms of an exposure-based integrated AD and PTSD intervention (i.e., COPE) when compared to a present-focused coping skills intervention (i.e., Seeking Safety [SS]) in male and female Veterans with comorbid AD and PTSD. Hypotheses for the primary aim are:

1. At post-treatment, both groups will show reductions in alcohol use, but COPE will demonstrate greater reduction in PTSD symptoms than SS.
2. At the 2nd and 3rd post treatment follow up assessment ,COPE will have significantly fewer percent drinking days than SS.
3. At the 2nd and 3rd post treatment follow up assessment ,COPE will continue to have lower PTSD symptom scores.

Design.

The proposed study will be a randomized controlled trial comparing Concurrent Treatment of PTSD and Substance Use Disorders using PTSD (COPE) to Seeking Safety (SS) for the treatment of male and female Veterans with AD/PTSD. 178 participants will be enrolled through the San Diego VA and randomized at the individual level. Measures will occur at baseline, post-treatment, and two post treatment follow up assessments. Participants will complete the 2nd post treatment assessment interview and set of questionnaires 3 months after the 1st post treatment appointment. Participants will be scheduled for their 3rd and last post treatment interview 3 months after completing their 2nd post treatment assessment. All procedures will be done for research purposes.

Methods

All work will be carried out at the SAMI outpatient program and PTSD clinics of the Veteran Affairs San Diego Healthcare Systems (VASDHS). Random permuted blocks will be used which ensure exactly equal treatment numbers at certain equally spaced points in the sequence of patient assignment. Randomization will be stratified by gender to ensure a balanced number of males and females are in each treatment group.

The Timeline Follow-back Procedure (TLFB50) will be employed at baseline, post-treatment, 5-month, and 8-month follow up to evaluate drinking and all drug use during the 30 days preceding each interview.

The Clinician-Administered PTSD Scale for DSM-V(CAPS54,55) is a standard semi-structured interview used to assess PTSD diagnosis and severity. As part of the CAPS, a list of potentially traumatic events is given to respondents.

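### The two-visit PTSD model names no covariance beyond a random intercept, so unequal variances combined with substantial month-2 dropout could distort the primary test

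*SAP*

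**What the plan says.** Section 6.H.3 of the SAP specifies, for the first primary aim, "a random intercept regression model with treatment condition (I-PE, SS) and a linear term for time (0, 2 months". It adds: "The primary test of the treatment conditions will be treatment x time interaction effect". With two visits, that contrast is the between-arm difference in change from baseline to month 2.

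The same paragraph describes the maximum-likelihood approach as "allowing modeling of the covariance error structure data across assessment points". It names no residual structure and gives no rule for choosing one.

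The missing-data text says that, if missingness is small and looks missing at random (MAR), the "maximum-likelihood analysis using all randomized cases and the observed data is an appropriate method for handling the missing data". It defines MAR broadly: "In the MAR model the missingness can be a function of the observed covariates and observed outcomes". It lists likely predictors of dropout: "Potential variables we will measure that may be related to study drop out are group assignment, social and familial support, employment status, and income". On sensitivity, it states: "we propose to perform MNAR sensitivity analyses using pattern mixture models".

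The protocol's Objectives describe the population as "male and female Veterans with comorbid AD and PTSD". Neither document gives an SD at either visit, a between-visit correlation or an expected dropout rate.

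**The concern.** With independent residuals, the usual default, a random intercept gives every visit the same variance. That need not hold here. Everyone enters with PTSD, which may narrow the spread of baseline scores, while month 2 is likely to mix responders and non-responders. A larger month-2 variance is therefore plausible, though the documents do not show it.

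The assumption matters because of how likelihood deals with missing scores. It in effect predicts an unseen month-2 score from the baseline score, using the model's own covariance. If that covariance is wrong, the prediction slope is wrong, and the fitted variance is a compromise between a smaller and a larger one. MAR does not protect against this, because likelihood inference under MAR needs the covariance to be right. At stake are the type I error of a primary test and, under some dropout patterns, its estimate.

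This is separate from whether the four-visit drinking model needs a random slope. Two visits cannot support a separately estimated random slope; the issue here is the equal-variance constraint.

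**Working it through.** **Inputs from the documents.** 178 participants (Protocol, Design) and equal allocation through permuted blocks (Protocol, Methods), hence 178/2 = 89 per arm. Model, contrast and ML handling of missing scores are as in the SAP.

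**Assumed inputs.** Baseline SD = 1; correlation 0.5; month-2 SD = k times baseline SD, with k from 0.75 to 2; month-2 dropout of 0, 20 or 30%; two-sided 5% test; no true effect. The plan has no figure of its own to reproduce on this point: 178 appears without alpha, power, effect size, SD or dropout.

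**Step 1: complete data.** Write s² for the common variance and r for the within-person correlation that the model fits. Its variance for a change score is 2s²(1 - r). At k = 1.5 the true variances are 1 and 2.25 and the covariance is 0.5 x 1.5 = 0.75. The model fits s² = (1 + 2.25)/2 = 1.625 and r = 0.75/1.625 = 0.46, so 2s²(1 - r) = 2 x (1.625 - 0.75) = 1.75. The true variance of change is 1 + 2.25 - 2 x 0.75 = 1.75. They agree, so the constraint does no harm.

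**Step 2: missing month-2 scores.** The true slope of month 2 on baseline is b = 0.5k. The model uses r instead (complete-data values shown):
- k = 1.25: b = 0.625; r = 0.625/[(1 + 1.5625)/2] = 0.49
- k = 1.5: b = 0.75; r = 0.46
- k = 0.75: b = 0.375; r = 0.375/[(1 + 0.5625)/2] = 0.48

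In each arm the estimated change is the mean of (month 2 - r x baseline) among those seen, plus (r - 1) times the mean baseline of everyone. Its expected error is (b - r) x D, where D is the mean baseline of those seen minus the mean baseline of all. The bias in the treatment contrast is therefore (b - r) x (difference in D between arms). It is zero if the variances are equal (b = r), if dropout is random (D = 0), or if dropout depends on baseline in the same way in both arms (the D values cancel).

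**Step 3: simulation.** 3000 runs per setting, random-intercept model fitted by REML. At 30% missing:

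| k | Model SE / true SE, random dropout | Type I error, random dropout | Bias (baseline SD), dropout rising with baseline in one arm only | Type I error, same pattern |
|---|---|---|---|---|
| 0.75 | 1.05 | 4.2% | +0.03 | 4.8% |
| 1 | 1.01 | 5.1% | 0.00 | 5.9% |
| 1.25 | 0.95 | 6.2% | -0.04 | 7.1% |
| 1.5 | 0.94 | 6.6% | -0.08 | 8.3% |
| 2 | 0.90 | 8.1% | -0.16 | 11.4% |

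Monte Carlo error is about 1.3% on the SE ratio and 0.4 points on type I error. With no missing data the SE ratio was 0.99-1.00 and type I error 4.3-5.6% at every k. With the same baseline-dependent dropout in both arms, bias was at most 0.01. If dropout depends on baseline in opposite directions in the two arms, an extreme pattern, bias at k = 1.25 and 1.5 was -0.08 and -0.17, with type I error of 7.9% and 13.4%.

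**Step 4: smaller amounts missing.** A separate ML simulation at k = 1.25-1.5 gave type I error of 4.8-6.2% and bias of at most about 0.01 SD at 5% missing. At 10% missing it gave 5.1-5.8% and, under arm-specific baseline-dependent dropout, 0.01-0.025 SD. Equal SDs gave 5.0-5.9% at the same rates.

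**Step 5: unstructured 2x2 covariance.** Across every setting in Step 3, bias was at most 0.01 SD, the SE ratio 0.97-1.02 and type I error 4.3-5.7%.

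**The case against.** Four points can fairly be made for the plan.

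First, the SAP says its approach permits modelling of the error covariance, so equal variances are not imposed. That stands to this extent: the defect is a structure left unspecified, not one that is forced. But the sentence describes a capability. If the structure is settled after the data are seen, the primary SE depends on a choice that was not prespecified, and the remedy is the same.

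Second, the SAP endorses ML only when missingness is small, and Step 4 shows little effect at 10% or less. This stands, and it limits the point to substantial dropout. The SAP, however, sets no threshold for small and offers no alternative primary analysis above it.

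Third, pattern-mixture models are planned. They are sensitivity analyses and leave the primary SE and test as they are.

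Fourth, every variance and dropout figure used here is assumed. This stands; neither the size nor the direction of any distortion can be established from the documents.

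A reader might infer that missing month-2 scores alone make the SE too small and bias the estimate, or that the bias favours the integrated arm (I-PE in the SAP, COPE in the protocol). The documents do not support either. At k = 0.75 the SE is too large. Bias needs both unequal variances and baseline-dependent dropout that differs by arm. Its sign follows the dropout pattern: at 30% missing and k = 1.5, reversing the dependence on severity in one arm moved the bias from -0.073 to +0.076 SD.

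**Conclusion.** The point holds in conditional form. Unless another residual structure is chosen, the first primary analysis assumes equal variances at 0 and 2 months, and the plan relies on that model to handle missing month-2 scores. The SE is distorted if the variances differ and dropout is substantial. Bias also requires arm-specific dependence of dropout on baseline, which the SAP's MAR definition allows; group assignment is among its own listed dropout predictors.

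For 89 per arm, correlation 0.5, SD ratio 1.25-1.5 and 30% missing, the SE is about 5-6% too small under random dropout. Type I error is mostly about 6-7.5%, reaching 8.3% in the worst one-arm setting tabulated. Bias under one-arm dropout is about 0.04-0.08 baseline SD in either direction. This is a cheap improvement of low-to-moderate priority; it does not show that the planned test is invalid.

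**What to change.** In SAP 6.H.3, first primary aim, replace the random intercept with an unstructured 2x2 within-person covariance (separate variances at 0 and 2 months and a free covariance). Fit it by REML with Kenward-Roger or Satterthwaite degrees of freedom. Keep treatment x time as the primary test.

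The cost is one sentence of SAP text, one line of code and one extra variance parameter. The complete-data contrast is unchanged. The reported SE may be slightly larger than under the random intercept when month-2 variance exceeds baseline variance.

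### The primary month-2 PTSD model leaves out the month-5 and month-8 PTSD scores, so a participant who misses month 2 but returns adds only a baseline outcome; a cheap fix gives a modest gain.

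*SAP*

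**What the plan says.** SAP section 6.H.3 states that the first primary aim is to "evaluate if I-PE will demonstrate greater reduction in PTSD symptoms than SS at post treatment". The model is a random intercept regression with treatment and "a linear term for time (0, 2 months"). "The primary test of the treatment conditions will be treatment x time interaction effect". For the second primary aim, percent days abstinent, the same section uses "a linear term for time (0, 2, 5, 8 months").

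The Protocol, under Design, says "Measures will occur at baseline, post-treatment, and two post treatment follow up assessments". The second post-treatment assessment comes 3 months after the first, and the third 3 months after that. With post-treatment at month 2, this gives 2 + 3 = 5 and 5 + 3 = 8 months. The same times appear under Methods for the drinking interview, which "will be employed at baseline, post-treatment, 5-month, and 8-month follow up". Hypothesis 3, under Objectives, is that at the two later assessments "COPE will continue to have lower PTSD symptom scores", so PTSD scores are needed there. (The SAP calls the experimental arm I-PE and the Protocol calls it COPE; I read them as the same arm.)

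The SAP's missing-data paragraph relies on maximum likelihood under MAR: "In the MAR model the missingness can be a function of the observed covariates and observed outcomes". It names arm, support, employment and income as possible dropout predictors. It also plans pattern-mixture models over three follow-ups as a sensitivity analysis.

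**The concern.** Maximum likelihood under MAR fills in a missing month-2 score from whatever else the model holds for that person. In a model of months 0 and 2, the only outcome left is the baseline score. The listed covariates may help, but none of them measures how the person's PTSD changed after randomization. Scores at months 5 and 8 do measure that, and they are already scheduled.

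Two things are at stake in the month-2 test. Precision is lost even when missingness is harmless. Bias that the later scores could partly remove is left in place if people who respond poorly skip the post-treatment visit, do so more in one arm than the other, and later return.

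**Working it through.** **Inputs from the documents.** 178 participants in equal blocks, so 178/2 = 89 per arm; visits at 0, 2, 5 and 8 months. The documents give no alpha, power, effect size, SD, dropout rate, return rate or within-person correlation, so 178 cannot be reproduced and every size below is conditional.

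**Assumptions.** SD 1 at every visit; fraction seen at month 2, q = 0.7 (missing p = 0.3); baseline–follow-up correlation ρ = 0.45; correlation between follow-ups φ = 0.6 or 0.75; a fraction r of those missing month 2 return for months 5 and 8. Covariance is treated as known.

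**1. Two-visit variance** of the between-arm month-2 change:

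V2 = (2/n) × [(1 − ρ²)/q + (1 − ρ)²] = (2/89) × [0.7975/0.7 + 0.3025] = (2/89) × 1.4418 = 0.0324, SE 0.18.

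**2. Four-visit variance**, visit as a category and treatment × visit, everyone seen at month 2 also having months 5 and 8:

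V4 = (2/n) × [τ²/q + (1 − ρ² − τ²)/(q + pr) + (1 − ρ)²],

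where τ² is the variance of the month-2 score given months 0, 5 and 8:

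τ² = (1 − ρ²) − 2(φ − ρ²)²/[(1 − ρ²) + (φ − ρ²)].

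- φ = 0.6: τ² = 0.7975 − 2(0.3975)²/1.195 = 0.533.
- φ = 0.75: τ² = 0.7975 − 2(0.5475)²/1.345 = 0.352.

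Example, φ = 0.6 and r = 0.25: q + pr = 0.775, and the bracket is 0.533/0.7 + 0.2645/0.775 + 0.3025 = 1.405. The ratio is 1.405/1.442 = 0.975, a cut of 2.5%.

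| Return fraction r | Variance cut, φ = 0.6 | Variance cut, φ = 0.75 |
|---|---|---|
| 0 | 0% | 0% |
| 0.10 | 1.1% | 1.8% |
| 0.25 | 2.5% | 4.3% |
| 0.30 | 3.0% | 5.0% |
| 0.50 | 4.6% | 7.8% |
| 0.70 | 6.0% | 10.2% |

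Some further loss at months 5 and 8 lowers these slightly, so about 2–4% at 25% return and 3–10% at 30–70%. At 25% return the gain is worth about 178 × (1/0.975 − 1) ≈ 5 to 178 × (1/0.957 − 1) ≈ 8 participants. Over a wider range (20–40% missing, follow-up correlations 0.5–0.8, 25% returning) the cut is 0.8–6.9%, and a two-sided 5% test with 80% power would move to 80.3–82.7%.

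**3. Bias in one arm** (large-sample normal ML, 30% missing, follow-up correlation 0.6, baseline correlation 0.4):

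| Month-2 missingness depends on | Two visits | Four visits, 25% return | Four visits, 50% return |
|---|---|---|---|
| Baseline score | 0.00 SD | 0.00 | 0.00 |
| Month-5 score | −0.11 SD | −0.07 | −0.05 |
| Unseen month-2 score | −0.22 SD | −0.20 | −0.18 |

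With no returners the two models agree in every row.

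**4. Bias in the arm contrast.** Assumed logit of missing month 2: −0.7 + 1.0 × month-2 deviation in COPE and −1.2 + 0.3 × deviation in SS. Correlations are as in steps 1–2, with 10% further loss at months 5 and 8. The two-visit model shows a spurious COPE benefit of about 0.18–0.20 SD. Four visits cut it by about 5–7% at 10% return and 13–38% at 30–70% return, leaving 0.19 × 0.87 ≈ 0.17 to 0.19 × 0.62 ≈ 0.12 SD in the latter range. With equal slopes of 0.65 in both arms the contrast bias is about zero in either model.

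**The case against.** The best defence is that a baseline and post-treatment model aims directly at the stated question, is valid under its own MAR assumption, and can report before month 8. Several parts of this stand.

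- A reader might infer that the planned test rests on MAR given baseline alone. It does not: the SAP calls for variables related to missingness and lists support, employment and income. The calculations above contain no such covariates and may overstate what later scores add.
- A reader might infer that the primary result will be biased. The documents contain nothing to show that dropout is informative or differs by arm, and do not say how many will miss month 2 and return. They say only that missing-data patterns can arise and that some will probably be small.
- Missingness driven by the unseen month-2 score is MNAR. The SAP acknowledges that possibility and plans pattern-mixture models for it.
- The four-visit model is not simply a weaker assumption, because it also needs missingness at months 5 and 8 to be ignorable. If worse-off participants return less often, the bias cut in step 4 drops to 2–4% at 10% return and 6–13% at 30%.

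What does not stand is that the gap is already closed. The pattern-mixture models are sensitivity analyses, and the dropout covariates are not PTSD scores, so neither brings months 5 and 8 into the primary fit. The SAP's phrase about using all observed data cannot be stretched to cover them either, since this model's times are explicitly 0 and 2.

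**Conclusion.** The point holds as a low-cost improvement. It is not a flaw that invalidates the primary test. The primary PTSD model ignores scheduled outcome data that bear on missing month-2 values.

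The precision gain is nil without returners, about 2–4% of variance at 25% return and about 3–10% at 30–70%, under the assumptions of 30% missing and the stated correlations.

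Any bias gain needs three conditions together: missingness related to PTSD beyond baseline and the modelled covariates, a difference between arms, and participants who return. In the assumed scenario of about 0.19 SD, the cut is about 5–7% at 10% return and 13–38% at 30–70%. It would be wrong to read the four-visit model as a cure for dropout: most of that bias remains, and those who never return add nothing. The direction is secure; the sizes depend on rates that the documents do not give.

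**What to change.** In SAP section 6.H.3, fit the primary PTSD model to all four visits (0, 2, 5 and 8 months) with visit as a category, treatment × visit terms and an unstructured covariance. Name the between-arm difference in change from baseline to month 2 as the single primary test. The month-5 and month-8 means stay free, so they do not shape the month-2 effect.

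Do not just extend the linear time term to month 8. That would test an average slope over 8 months, which is a different question from the post-treatment one.

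Keep the dropout covariates and the pattern-mixture sensitivity analyses.

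The cost is SAP wording, no new data, and some parameters: 8 arm-by-visit means instead of 4, and 4 × 5/2 = 10 covariance parameters instead of the 2 of a random intercept model. The primary analysis must also wait for month-8 data.

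### The first primary PTSD test is in effect a change-score comparison; adjusting for baseline would estimate the same effect at least as precisely, at almost no cost

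*SAP*

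**What the plan says.** SAP 6.H.3 specifies the first primary analysis in these words: "The statistical model will be a random intercept regression model with treatment condition (I-PE, SS) and a linear term for time (0, 2 months"). It then says: "The primary test of the treatment conditions will be treatment x time interaction effect". Baseline PTSD score is not a covariate, and nothing holds the two arms to a common baseline mean.

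Covariate adjustment is optional: "The model can be expanded to determine an adjusted intervention effect by including additional covariates(e.g., age, ethnicity"). The section describes the likelihood approach as "allowing modeling of the covariance error structure data across assessment points". The missing-data text of the SAP plans a "maximum-likelihood analysis using all randomized cases and the observed data", provided missingness is small and consistent with missing at random.

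On gender, the Protocol (Methods) says "Randomization will be stratified by gender to ensure a balanced number of males and females are in each treatment group", and SAP 6.H.3 adds a moderation test: "We will also test the extent to which gender moderates treatment effect". Gender is not otherwise a term in the primary model.

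The Protocol (Design) gives the sample size: "178 participants will be enrolled through the San Diego VA and randomized at the individual level". Neither document gives an SD, a baseline-to-post correlation, a dropout rate, a target effect or a power.

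**The concern.** A treatment x time term over only two visits carries no more information than a comparison of change scores. A change score subtracts the whole baseline value, which is the best weight only when the slope of post-treatment score on baseline happens to be 1. When the slope is below 1, subtraction over-corrects. It adds baseline noise to the estimate, and a chance baseline difference between arms passes partly into the result.

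What is at stake is precision on the first primary result. The confidence interval may be wider than the same 178 patients can support. There is no bias to correct, and no shortfall against a stated power can be claimed because none is stated.

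**Working it through.** **Inputs.** From the documents: N = 178, taken as 89 per arm because the permuted blocks aim at equal numbers; visits at months 0 and 2; a random intercept; maximum likelihood. Assumed: correlation ρ = 0.3, 0.5, 0.7; post/baseline SD ratio k = 0.8 to 1.5; share of post scores missing m = 0 or 0.3, completely at random. The documents contain no precision or power figure to reproduce.

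**Identity.** On one simulated complete data set (N = 178, ρ = 0.5), the fitted interaction multiplied by 2 months was −0.2746 with SE 0.1451. Ordinary regression of change on arm gave the same estimate and SE. Adding a baseline covariate as a main effect changed neither, so the optional age and ethnicity terms, entered that way, would not recover the lost precision.

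**Variances.** Per arm, in squared baseline-SD units and multiplied by n:

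- Baseline-adjusted: A = k²(1 − ρ²)/(1 − m)
- Planned, separate baseline means: P = A + (1 − ρk)²
- Information lost = 1 − A/P; confidence interval widening = √(P/A) − 1

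The loss is zero only where ρk = 1. For k = 1 and m = 0 it reduces to (1 − ρ)/2.

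*Worked case, k = 1, ρ = 0.5, complete data.* A = 0.75 and P = 0.75 + 0.25 = 1.00. The loss is 25% and the interval is √(1/0.75) − 1 = 15% wider. Comparing post-treatment scores alone also has variance 1.00, so here the planned test does no better than ignoring baseline.

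*Same case, 30% missing.* A = 0.75/0.7 = 1.071 and P = 1.321. The loss is 19% and the interval is 11% wider.

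Information lost:

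| SD ratio k, missing m | ρ = 0.3 | ρ = 0.5 | ρ = 0.7 |
|---|---|---|---|
| 0.8, none | 50% | 43% | 37% |
| 1.0, none | 35% | 25% | 15% |
| 1.0, 30% | 27% | 19% | 11% |
| 1.2, none | 24% | 13% | 3% |
| 1.5, none | 13% | 4% | 0.2% |

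For k = 1 the interval is 24, 15 and 8% wider with complete data, and 17, 11 and 6% wider with 30% missing. With k = 1 and no missing data, an adjusted analysis would match the planned precision with 178 × 0.65, 0.75 or 0.85, that is about 116, 134 or 152 patients.

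**Simulation.** In 20,000 trials per ρ (k = 1, complete data, true difference −0.40), both methods averaged −0.40. The variance ratios, adjusted to planned, were 0.65, 0.74 and 0.85, against 0.65, 0.75 and 0.85 from the formula.

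**Cost of adjusting.** Estimating the slope inflates the variance by about 1/(178 − 4) = 0.6%. This matters only where the gain is near zero.

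**Chance imbalance.** The SE of the baseline difference is √(2/89) = 0.15 SD. An imbalance of 1.96 SE is 0.29 SD. With equal SDs it shifts the change-score estimate by (1 − ρ) × 0.29 = 0.21, 0.15 or 0.09 SD. Over all randomisations these shifts average zero.

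**A trap in the remedy.** Constraining the baseline means while keeping only a random intercept forces equal SDs at both visits. The weight on baseline becomes b = 2ρk/(1 + k²), with variance k² − 2bρk + b², against 1 + k² − 2ρk for the planned test. At k = 1.5 the ratio is 1.771/1.750 = 1.01 for ρ = 0.5 and 1.311/1.150 = 1.14 for ρ = 0.7, which is worse than the plan.

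**Gender.** A gender main effect leaves the planned test unchanged (in a simulated fit, −0.1176 with SE 0.1367 both with and without it). After baseline adjustment the gain is G/(1 − ρ² + G), where G = p(1 − p) × gap² × (1 − ρ)². Assuming 10–20% women and a constant gap of 0.3–0.5 SD, that is about 0.1–2%.

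**The case against.** The strongest reply is that the plan contains no error. A pre-specified treatment x time interaction under maximum likelihood is a standard way to test for greater symptom reduction, and it is unbiased. That is correct, and it makes this a recommendation about efficiency.

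The second reply is that the size is not anchored in the documents. Everyone enters with PTSD, so baseline scores may be range-restricted and post scores more spread out, giving an SD ratio above 1. At a ratio of 1.5 the loss is only 13, 4 or 0.2%. This stands as a limit on the claimed size: the gain may be material or negligible. Range restriction could also lower the correlation, which works the other way.

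Third, the formula for P describes the planned random-intercept model exactly only with complete data or equal SDs. With missing data and unequal SDs it describes an unstructured covariance. This is correct, but the discrepancy favours adjustment. At k = 1.5, ρ = 0.7 and 30% missing, the loss against the random-intercept fit is about 5%, against about 0.2% from the formula.

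Fourth, using baseline as a covariate drops patients with no post score, whereas the SAP plans to use all randomised cases. The constrained mixed model does fit that wording better. With one post-treatment visit and data missing at random, though, the covariate version loses essentially no information on the treatment effect.

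Finally, the posted SAP text begins at 6.H.3, so SDs or power may be given in sections that cannot be seen here.

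**Conclusion.** The point holds as an efficiency weakness in a valid analysis. Across the complete-data grid the information lost runs from 50% down to 0.2%, and it is 15–35% if the SDs are equal. Every SD, correlation and missingness value behind those figures is assumed. The adjusted analysis targets the same effect because randomisation equalises the expected baseline means, and its only statistical cost is about 0.6% in variance. The change should be made because it needs no new data and protects the first primary result against chance baseline imbalance. The gender point is minor and separable.

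**What to change.** In SAP 6.H.3, define the primary PTSD estimate as the month-2 arm difference, obtained in one of two ways:

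- the maximum-likelihood mixed model with baseline means constrained equal across arms and an unstructured 2×2 visit covariance, which fits the SAP's all-randomised-cases approach most directly; or
- a regression of the month-2 score on arm with baseline score as a covariate.

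State explicitly that the constraint is not to be combined with a random intercept alone. Include gender and gender x visit as fixed effects in the mixed model, or gender as a covariate in the regression, and keep the gender moderation test as a separate analysis. No change to the drinking model is proposed here.

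The cost is wording only. The month-0 score and gender are already collected, and the SAP already allows the covariance across visits to be modelled. The change should be made before outcomes are seen by arm; if they have been seen, report the adjusted estimate as supplementary and keep the planned test as primary.

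### The protocol's second hypothesis concerns percent drinking days, but the SAP's second primary aim tests abstinence from any substance use, which is a different variable

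*SAP*

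**What the plan says.** **Protocol (04/14/2016), Objectives.** The primary aim concerns alcohol and PTSD: "The primary aim will be to evaluate the effects on alcohol use and PTSD symptoms". Hypothesis 2 is that "COPE will have significantly fewer percent drinking days than SS" at the second and third post-treatment assessments.

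**Protocol, Methods.** The TLFB is used at every assessment "to evaluate drinking and all drug use during the 30 days preceding each interview".

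**SAP (09/03/2011), section 6.H.3.** The second primary aim asks whether I-PE, the SAP's label for the exposure-based arm, gives "greater percent days abstinent (PDA) from substance use at 5 and 8-month follow-up". The model is a random intercept regression over months 0, 2, 5 and 8, and "The primary test of the treatment conditions will be the treatment x time interaction effect".

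The visits agree. The protocol spaces the later assessments three months apart, and 2 + 3 = 5 and 5 + 3 = 8. Only the outcome variable differs.

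**The concern.** Two changes separate the protocol's variable from the SAP's. Going from drinking days to abstinent days only reverses the sign. Going from drinking to substance use changes what is counted, because the TLFB captures drugs as well as alcohol.

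Read literally, section 6.H.3 contains no alcohol-only analysis, so hypothesis 2 has no specified primary test. A participant who stops drinking but still uses a drug on those days improves under the protocol and shows no change under the SAP. The same TLFB data can thus support different conclusions. With no rule of precedence between the documents, the choice of primary variable could be made after results are known.

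**Working it through.** The plan states no figure that depends on this definition. It gives N = 178 but no alpha, power, effect size, SD or drug-use rate, so there is nothing to reproduce and no power loss can be derived. What can be derived is the exact relation between the two variables.

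**Input from the documents:** a 30-day TLFB window covering drinking and all drug use (protocol, Methods).

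**Definitions, per participant and window.** Let A be the days with any alcohol and D the days with drug use but no alcohol (drug-only days).

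- Percent drinking days: PDD = 100 × A/30
- Percent days abstinent from alcohol = 100 × (30 − A)/30 = 100 − PDD
- Percent days abstinent from any substance: PDA = 100 × (30 − A − D)/30 = 100 − PDD − 100 × D/30

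Drug use on a drinking day changes neither score. Each drug-only day lowers PDA by 100/30 = 3.3 points and leaves PDD as it was. The two are complements only when D = 0.

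**Example (assumed counts).** With A = 6 and D = 3, PDD = 20.0, alcohol-only abstinence = 80.0 and any-substance abstinence = 100 − 20.0 − 10.0 = 70.0.

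**Effect on the treatment contrast.** Take the change from baseline and subtract SS from COPE, signed so that positive favours COPE:

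SAP effect = alcohol effect − (100/30) × k,

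where k is the change in drug-only days in COPE minus the change in SS. A difference between arms that is constant over time gives k = 0 and drops out of the treatment × time test.

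**Illustration 1 (all inputs assumed).** COPE cuts drinking by 3 days per 30 more than SS, an alcohol effect of 100 × 3/30 = 10.0 points.

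| k (days) | SAP effect = 10.0 − 3.33k (points) |
|---|---|
| −1 | 13.3 |
| 0 | 10.0 |
| +1 | 6.7 |
| +3 | 0.0 |
| +4 | −3.3 |

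**Illustration 2 (all inputs assumed).** A share q of the drinking days removed remain drug-use days, equally in both arms. The SAP effect is then 10.0 × (1 − q).

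| q | SAP effect (points) |
|---|---|
| 10% | 9.0 |
| 20% | 8.0 |
| 40% | 6.0 |

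**The case against.** The strongest objection is that substance use in the SAP may be shorthand for alcohol. The SAP's title refers to alcohol disorder, and the protocol gives COPE a full name that mentions substance use disorders while enrolling patients with alcohol disorder. On that reading PDA = 100 − PDD exactly, and only the wording is at fault. The SAP supplied is also a single numbered subsection, so a definition may exist elsewhere in the parent plan. This reading is possible but less natural, because the protocol separates drinking from all drug use when it describes the instrument. Since the text does not settle the matter, the definition has to be written down on either reading.

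A second objection concerns magnitude, and part of it stands. Only the 3.3 points per day comes from the documents. A reversal of sign needs drug-only days to rise by more than the drinking days removed (k above 3 in the first illustration). It is a mathematical possibility with no figure in the plan behind it. Partial substitution, as in the second illustration, shrinks the effect but cannot reverse it. Equal change in drug-only days across arms is enough for the discrepancy to vanish; the levels need not be equal.

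A third objection is that the SAP is simply older, as its date and the I-PE label suggest, and that the later protocol is clear. That probably explains the conflict, but neither document says that the protocol overrides the SAP.

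**Conclusion.** The concern holds. Followed as written, the SAP tests a different second primary variable from the one in the protocol's hypothesis 2. The gap is 3.3 points for each drug-only day in the 30-day window, and the treatment effect shifts by 3.3 points for each day by which the arms differ in their change in drug-only days.

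This rests on reading substance use as alcohol plus drugs. The consequence for the trial's result cannot be sized from the documents. It is nil if drug-only days are absent or change equally in both arms. What is certain is that the identity of a primary variable is open until one is named.

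**What to change.** Before outcome data are examined by arm, issue a dated SAP revision that:

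1. defines the second primary variable as percent drinking days from the 30-day TLFB (days with any alcohol / 30 × 100), or equivalently percent days abstinent from alcohol, to match the protocol's primary aim and hypothesis 2;
2. lists percent days abstinent from alcohol and all drugs as a named secondary outcome.

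The first item is the essential one. The second keeps the SAP's existing variable in view without leaving two candidates for the primary test. If outcomes have already been examined by arm, report both variables and state which document specified each.

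The cost is a wording change and one additional secondary analysis. Both variables come from the same TLFB records, so no new data are needed.
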